AUC	Area under plasma concentration-time curve from zero to infinity
AUC _{0-t}	Area under plasma concentration-time curve from zero to the last measurable time point
AUC _{0-τ}	Area under plasma concentration-time curve over the dosing interval, τ
bd	Twice daily (Latin: bis die)
BP	Blood pressure
C _{avg}	Average plasma drug concentration over the dosing interval
C _{ss,avg}	Average plasma drug concentration over the dosing interval at steady state
CI	Confidence interval
CL/F	Apparent plasma clearance following oral administration
CL _{ss} /F	Apparent plasma clearance following oral administration at steady state
C _{max}	Maximum plasma drug concentration
C _{ss,max}	Maximum plasma drug concentration at steady state
C _{ss,min}	Minimum plasma drug concentration at steady state
CRF	Case record form
CSR	Clinical Study Report
CTC	Common terminology criteria (derived from National Cancer Institute Common Terminology Criteria for Adverse Events (NCI CTCAE) Version 4)
CV	Coefficient of variation
dECG	Digital electrocardiogram
ECG	Electrocardiogram
FI	Fluctuation index
%GCV	Geometric %CV
IP	Investigational Product
LOQ	Limit of quantification
λ _z	Terminal rate constant
MedDRA	Medical Dictionary for Regulatory Activities
NC	Not calculable
NQ	Non quantifiable
PD	Pharmacodynamics
PK	Pharmacokinetics
PR	PR interval of ECG
QRS	QRS interval of ECG

Abbreviation or special term	Explanation
QT	QT interval of ECG
QTc	QT interval corrected for heart rate
QTcB	QT interval corrected for heart rate using Bazett's correction
QTcF	QT interval corrected for heart rate using Fridericia's correction
QTcI	QT interval corrected for heart rate using individual-specific correction
R&D	Research and Development
RR	RR interval of ECG
SAE	Serious adverse event
SD	Standard deviation
$t_{1/2}$	Terminal half-life
t_{max}	Time to reach maximum plasma concentration
$t_{ss,max}$	Time to reach maximum plasma concentration at steady state
$t_{ss,min}$	Time to reach minimum plasma concentration at steady state
V_z/F	Apparent volume of distribution

AMENDMENT HISTORY

Date	Brief description of change
6 May 2014	Update to Global Product Statistician signatory.
Edition Number 2.0	ECG categories updated in section 4.2.4 . Updated Table 2 to include steady state / multiple dose PK parameters. Updated list of abbreviations with steady state PK parameters.
8 May 2014	Updated date format on page 1.
Edition Number 2.1	Replaced '6 th May 2014' on signature pages with 'Date'.

1. STUDY DETAILS

1.1 Study objectives

Primary objective

- To investigate the effect of food on the pharmacokinetics (PK) of olaparib following oral dosing of the tablet formulation in patients with advanced solid tumours.

Secondary objectives

- To investigate the effect of olaparib on the QT interval corrected for heart rate (QTc) following single (Part A) and multiple (Part B) oral dosing of the tablet formulation in patients with advanced solid tumours.
- To assess the safety and tolerability of olaparib following oral dosing of the tablet formulation in patients with advanced solid tumours.

1.2 Study design

This is a 3-part study in patients with advanced solid tumours:

- Part A will determine the effect of food on the PK of olaparib and the effect of olaparib on the QT interval following a single oral dose of olaparib tablets;
- Part B will determine the effect of olaparib on the QT interval following multiple oral dosing of olaparib tablets;
- Part C will allow patients continued access to olaparib tablets after the PK and QT phases (Parts A & B) and will provide for additional safety data collection.

A total of 48 patients are planned to be enrolled at approximately 8 sites in Western Europe; approximately 42 evaluable patients will be expected to complete the study.

Part A of this study is a randomised, open-label, 2-treatment period crossover study in approximately 48 patients with advanced solid tumours. Each patient will receive a single oral dose of olaparib tablets 300 mg in each of 2 treatment periods (once in the overnight fasted state and once immediately following a high-fat meal at breakfast time), with at least 5 and no more than 14 days (washout) between doses. Digital ECG (dECG), PK assessments, and safety assessments will be obtained for up to 72 hours post-dose in each treatment period. Additionally, during the first treatment period, patients will undergo baseline dECG assessments on Day -1 (ie, the day prior to dosing) at clock times matched to planned/scheduled dECG assessment times on the dosing day (Day 1). Patients will check into the clinic on the evening of Day -2 (first treatment period) or the evening of Day -1 (second treatment period) and remain resident until 24 hours after each dose of olaparib tablets (Day 2). The dECGs performed on Day 1 in each treatment period will be clock-

matched to the actual times that the Day -1 dECGs are performed in the first treatment period. Patients will return to the clinic for assessments on Days 3 and 4 of each treatment period. On Day 1 of Part A patients should be fasted over the same time period as Day -1.

Part B of this study is an open-label study in the same patients who participated in Part A. Upon completion of Part A, following a washout period (of at least 5 days and no more than 14 days between the last dose in Part A and Day -1 of Part B) and providing the patient continues to meet the study entry criteria, each patient will receive olaparib tablets 300 mg bd for 5 days. Patients will check into the clinic on the evening of Day -2. On Day -1, baseline dECG assessments will be performed at clock times matched to planned/scheduled dECG assessment times on Day 5. Patients will be discharged from the clinic on the evening of Day -1. Patients will self-administer their olaparib doses under fasted conditions (from 1 hour prior to 2 hours after the olaparib dose) from Day 1 up to the morning of Day 4 on an outpatient basis. On the evening of Day 4, patients will check back into the clinic, and will receive their Day 4 evening dose. On the morning of Day 5, patients will receive their Day 5 morning dose after an overnight fast and will remain fasting for 4 hours post-dose. Patients will undergo dECG and PK assessments pre-dose and for 12 hours post-dose. The dECGs performed on Day 5 will be clock-matched to the actual times that the Day -1 dECGs are performed. Patients will be discharged from the clinic after completing 12-hour assessments on Day 5, and will self-administer their evening Day 5 dose of olaparib tablets. On Day 5 of Part B patients should be fasted over the same time period as Day -1.

On completion of Part B, patients may be entered into Part C and continue to take olaparib tablets (300 mg bd) if they and the investigator agree that this is appropriate. Patients should start Part C immediately after the last dose received in Part B. Patients will have weekly clinic visits for the first 4 weeks; thereafter visits will be every 4 weeks. Part C will be of 12 months' duration from the date the last patient enters this part of the study.

During and after Part C, patients may continue to take olaparib tablets. After the end of Part C patients will be seen as per their normal routine clinical schedule and no clinical data will be collected, other than serious adverse events (SAEs) and drug dispensing/accountability.

Patients will return to the clinic for follow-up assessments either 30 days (± 7 days) after their last dose (regardless of whether the last dose is in Part A, Part B, Part C, or the continued access phase after Part C). If a patient discontinues olaparib tablets during Part C, they will also attend a study treatment discontinuation visit.

Patients aged ≥ 18 years with advanced solid tumours who are refractory to standard therapy and are able to eat a high-fat meal will be recruited.

1.3 Number of patients

The study has been sized to provide an estimate of the difference between olaparib PK parameters in the fed and fasted states. Based on the estimate of within-patient standard deviation (SD) for log AUC from Studies D0180C00002 and D0180C00003 of 0.26, and assuming a true food effect difference of 5%, 42 evaluable volunteers (21 per-sequence) will

give 90% power of showing that the 90% confidence interval (CI) for the food effect (ratio of geometric least-squares means of AUC or C_{max} in the fed state to the fasted state) lies entirely within the range of 0.8 to 1.25.

A total of 48 patients will be entered to ensure that 42 evaluable patients complete the study. nQuery v7.2 was used for the sample size calculations.

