4.2.3 Food effect analysis (Part A only)

Following log-transformation using natural logarithms, C_{max} , AUC and AUC_{0-t} will be analysed using a mixed effect analysis of variance (ANOVA) model, fitting terms for sequence, patient within sequence, period and treatment (where treatment represents food condition i.e. fed or fasted). Patient within sequence will be treated as a random effect in the model.

Point estimates and adjusted 90% CIs for the difference between treatments, for C_{max} , AUC and AUC_{0-t} , will be constructed based on the following treatment comparisons:

- Fed compared to Fasted

Each confidence interval will be based on the t distribution. The sum of squares of the residuals in the linear model will be used to estimate the variance, which is assumed to be equal for both treatments.

The point estimate and adjusted 90% CIs will then be exponentially back transformed to provide point and confidence interval (CI) estimates for the ratio of interest. No food effect on the PK of olaparib will be concluded if the 2-sided 90% CIs for the ratios of AUC (or AUC_{0-t} as previously noted) and C_{max} are within the range of 0.80 to 1.25.

The analysis will be performed using SAS procedure MIXED in the following manner:

```
PROC MIXED DATA=;
```

```
CLASS patient sequence period treatment;
```

```
MODEL logY=sequence period treatment;
```

```
RANDOM patient(sequence);
```

ESTIMATE 'Fed vs. Fasted' treatment -1 1 / CL ALPHA=0.10;

RUN;

QUIT;

Where logY is log(AUC), log(C_{\max}) and log(AUC_{0-t}) and treatment is coded as 0 = "Fed" and 1 = "Fasted".

Assumptions of normality and constancy of variance will be explored in all analyses and, if necessary, an appropriate transformation (eg, rank) or non-parametric technique (eg, Mann-Whitney test) will be used to validate the results of the main analysis.

Results of this analysis will be presented in an overview table. The original SAS output of this PROC MIXED will be presented in an additional appendix.

An analysis of t_{\max} using the Wilcoxon Signed Rank Test, and the Lehmann median estimator of difference and 90% CIs will also be presented for the following treatment comparisons:

- Fed compared to Fasted

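### The 90% power in SAP section 1.3 is for one PK parameter, but section 4.2.3 needs both AUC and Cmax to pass; on the plan's own inputs the power for that rule is about 82-89%

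*SAP*

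**What the plan says.** SAP section 1.3 takes its only variance input from AUC: "Based on the estimate of within-patient standard deviation (SD) for log AUC from Studies D0180C00002 and D0180C00003 of 0.26". It then goes on "assuming a true food effect difference of 5%, 42 evaluable volunteers (21 per-sequence) will" reach the stated power, which is to "give 90% power of showing that the 90% confidence interval (CI) for the food effect" stays inside the limits 0.8 to 1.25. The food effect is defined there as the "ratio of geometric least-squares means of AUC or C_{max} in the fed state to the fasted state", which is one ratio at a time. The section gives neither an SD for log Cmax nor a correlation between the two parameters, and it does not say whether the 5% is an increase or a decrease.

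Section 4.2.3 sets the decision rule: "No food effect on the PK of olaparib will be concluded if the 2-sided 90% CIs for the ratios of AUC" (or AUC0-t where AUC cannot be estimated adequately) and Cmax fall within 0.80 to 1.25. Both intervals must meet the limits.

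**The concern.** The event that was powered and the event that decides the primary objective are different. Section 1.3 gives the chance that one interval falls inside the limits; section 4.2.3 needs two. The chance that both pass can never be larger than the chance for either alone, and it is smaller unless the second parameter passes whenever the first does.

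A reader who takes 90% as the chance of reaching the no-food-effect conclusion, given a true 5% effect, would be too optimistic. The risk of missing the conclusion would be taken as about 10%. On the plan's own inputs it is about 11-18%.

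**Working it through.** **Inputs from the SAP.** Section 1.3: within-patient SD 0.26 (log scale, AUC), true effect 5%, 42 evaluable patients in a two-period crossover with 21 per sequence, limits 0.80 to 1.25. Section 4.2.3: two-sided 90% CI based on the t distribution, which amounts to two one-sided tests at 5% each; AUC and Cmax must both pass.

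**Step 1: reproduce the stated figure for one parameter.**
- Standard error of the log ratio: 0.26 × √(2/42) = 0.0567.
- Degrees of freedom: 42 − 2 = 40; t(0.95, 40) = 1.684. Expected half-width of the 90% CI: 1.684 × 0.0567 = 0.0955.
- Limits on the log scale: ±ln 1.25 = ±0.2231.
- Distance from the true value to the nearer limit: 0.2231 − ln 1.05 = 0.2231 − 0.0488 = 0.1744 for ratio 1.05, or 0.2231 − |ln 0.95| = 0.2231 − 0.0513 = 0.1719 for ratio 0.95.
- In standard errors: 3.07 and 3.03. Subtracting 1.684 leaves 1.39 and 1.35, so a normal approximation gives about 0.92 and 0.91.
- Exact power, integrating over the chi-square distribution of the residual variance: **0.914** (ratio 1.05) and **0.908** (ratio 0.95).

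The 90% is therefore correct for a single parameter with SD 0.26.

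**Step 2: power for the rule in section 4.2.3.** Assume that 0.26 and 5% hold for Cmax as well, with the effect in the same direction. With independent parameters the joint power is the product: 0.914² = 0.836 and 0.908² = 0.824. With correlation, the two log-ratio estimates were simulated as bivariate normal and the residual variances as Wishart with 40 degrees of freedom (400,000 draws):

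| Within-patient correlation of log AUC and log Cmax | Ratio 1.05 | Ratio 0.95 |
|---|---|---|
| 0 | 0.84 | 0.82 |
| 0.5 | 0.85 | 0.84 |
| 0.75 | 0.87 | 0.86 |
| 0.9 | 0.89 | 0.88 |

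**Step 3: what would bring the joint power to 0.90?** The ceiling is the AUC power itself, about 0.91.
- *Correlation, both SDs 0.26.* At ratio 1.05 the joint power is 0.8995 at correlation 0.97 and 0.9025 at 0.98. At ratio 0.95 it is still 0.898 at 0.99.
- *A smaller Cmax SD.* With Cmax SD 0.20 the joint power at correlation 0 is 0.905 (ratio 1.05) or 0.896 (ratio 0.95). With Cmax SD 0.22 and correlation 0.8 it is 0.908 or 0.900. So the Cmax SD has to be about 0.20-0.22, clearly below 0.26, and slightly lower still at ratio 0.95 with no correlation.

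**The case against.** The strongest reply is that section 1.3 contains no calculation error. It speaks of AUC or Cmax, one ratio at a time, and its 90% is right for that; it never claims a joint power. This stands. The fault is that the figure given is not the one that matches the rule, not that the figure is miscalculated.

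Three stronger readings are tempting, and the SAP does not support them:
- *That the power for the rule is below 90% in every case.* The SAP gives no Cmax SD and no correlation. Because AUC power is slightly above 90%, the joint power can be 0.90-0.91 if Cmax is clearly less variable than AUC. What holds without further assumption is only the ceiling of about 0.91.
- *That the shortfall is much larger because Cmax is more variable than AUC.* That may be so, but nothing in the SAP gives a Cmax SD above 0.26, so figures for larger SDs have no basis here.
- *That missing the limits on Cmax would be taken as proof of a food effect.* Section 4.2.3 says only when no food effect is concluded. Point estimates and 90% CIs are reported for Cmax, AUC and AUC0-t, so an imprecise result would be visible.

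Two further points are fair. Section 1.3 opens by describing the sizing as a matter of estimating the fed-fasted difference; yet the same paragraph justifies 42 by the chance of meeting the limits, and section 4.2.3 applies those limits. Also, 48 patients are to be entered. If all 48 were evaluable, joint power with SD 0.26 for both would be 0.88-0.92 (correlation 0 to 0.9), but the plan's power statement relies on 42. Finally, the protocol, which is not at hand, may give a Cmax SD; its absence from the SAP is not in itself the fault.

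**Conclusion.** The point holds in a conditional form. The stated 90% is right for one parameter with SD 0.26 (0.914 or 0.908), but it does not carry over to the rule that AUC and Cmax must both pass. With 0.26 and 5% applied to both parameters and 42 evaluable patients, the power of that rule is about 0.84-0.89 at ratio 1.05 and 0.82-0.88 at ratio 0.95, a loss of roughly 1 to 8 percentage points against the stated 90%. The range rests on three assumptions: the Cmax SD equals the AUC SD, both effects are 5% in the same direction, and the correlation lies between 0 and 0.9. Outside them the joint power could reach 0.90-0.91, but not more.

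Because both parameters must pass, type I error is not inflated. The consequence is a stated power that is somewhat too favourable for the trial's primary conclusion, and no analysis result would change.

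**What to change.** Restate section 1.3 along these lines: *With a within-patient SD of 0.26 for log AUC and a true fed/fasted ratio of 0.95 or 1.05, 42 evaluable patients give about 91% power for AUC alone. Power for the rule in section 4.2.3, under which AUC and Cmax must both meet the limits, is about 82-89% if the within-patient SD of log Cmax is also 0.26, for a true ratio of 0.95 or 1.05 in both parameters and a correlation between them of 0 to 0.9.*

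If the two source studies provide a within-patient SD for log Cmax and its correlation with log AUC, replace the range with the joint power computed from those values.

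Leave the sample size, the model and the decision rule as they are. The cost is a short change of SAP wording and a slightly less favourable stated figure.

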2. ANALYSIS SETS

2.1 Definition of analysis sets

There will be 3 analysis sets considered in this study:

- The safety analysis set will include all patients who receive at least one dose of olaparib.
- The PK analysis set will include all patients who receive an olaparib dose and provide evaluable PK profiles in at least 1 treatment period i.e. fed (A) or fasted (A).

If a patient has a major protocol deviation that affects the evaluability of the PK profile in any treatment period, then the patient will not form part of the PK analysis for that treatment period.

- The QT analysis set will include all patients who have at least 1 evaluable time-matched QT/QTc interval value at a scheduled time point, time-matched between Day -1(baseline) and Day 1(treatment periods 1 or 2) for Part A, or time matched between Day -1(baseline) and Day 5 for Part B.

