2.2 Violations and deviations

Important protocol deviations will be agreed by the study team physician, pharmacokineticist and statistician before any statistical analysis is performed.

Patients who withdraw from the study following dosing, but prior to study completion, will be included in the PK analysis provided they have evaluable profiles over the planned collection period. Patients with partial data will be evaluated on a case-by-case basis to determine if sufficient data are available for meaningful analysis.

If a patient vomits within approximately 3 hours after dosing with olaparib tablets, all PK sampling may be omitted for that treatment period but the safety assessments should continue as per the study schedule. The patient may continue in the study and proceed with Part A, if applicable, and then on to Part B and Part C.

Important protocol deviations include changes to the procedures that may impact the quality of the data, or any circumstances that can alter the evaluation of the PK. Examples include,

but may not be limited to, vomiting following oral dosing occurring within the time frame of 2 times the median t_{\max} , sample processing errors that lead to inaccurate bioanalytical results, incomplete dose administered, incomplete PK profile collected, and/or use of disallowed concomitant medication. In the case of an important protocol deviation, affected PK data collected will be excluded from the summaries and statistical analyses, but will still be reported in the study result listings. Important deviations will be listed and summarised in the Clinical Study Report (CSR).

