3. PRIMARY AND SECONDARY VARIABLES

Primary variables

The primary PK outcome variables to be calculated for olaparib are described below. All PK parameters for Parts A & B will be summarised descriptively. For Part A, AUC, (or AUC_{0-t} , if AUC is not adequately estimable), C_{\max} and t_{\max} will also be statistically analysed.

- Single-dose PK parameters will be calculated for olaparib during each treatment period in Part A:
 - C_{\max} Maximum plasma concentration obtained directly from the observed concentration versus time data
 - t_{\max} Time to maximum plasma concentration obtained directly from the observed concentration versus time data
 - AUC_{0-t} Area under the plasma concentration-time curve from zero to the time of the last measurable concentration, calculated by linear up/log down trapezoidal summation
 - λ_z Terminal rate constant estimated by log-linear least squares regression of the terminal part of the concentration-time curve
 - AUC Area under the plasma concentration-time curve from zero (pre-dose) extrapolated to infinity calculated by linear up/log down trapezoidal summation and extrapolated to infinity by the addition of the last quantifiable concentration divided by the terminal rate constant: $AUC_{0-t} + C_{\text{last}}/\lambda_z$
 - $t_{1/2}$ Terminal half-life. Visual assessment will be used to identify the terminal linear phase of the concentration-time profile
 - CL/F Apparent plasma clearance
 - V_z/F Apparent volume of distribution
- Multiple-dose PK parameters will be calculated for olaparib on Day 5 of Part B:

- $C_{ss,max}$ Maximum plasma concentration obtained directly from the observed concentration versus time data
- $t_{ss,max}$ Time to maximum plasma concentration obtained directly from the observed concentration versus time data
- $C_{ss,min}$ Minimum plasma concentration obtained directly from the observed concentration versus time data
- $t_{ss,min}$ Time to minimum plasma concentration obtained directly from the observed concentration versus time data
- $AUC_{0-\tau}$ Area under the plasma concentration-time curve over the dosing interval, τ , calculated by linear up/log down trapezoidal summation
- $C_{ss,avg}$ Average concentration over the dosing interval calculated as $AUC_{0-\tau}/\tau$
- FI Fluctuation index, calculated as $[(C_{ss,max}-C_{ss,min})/C_{ss,avg}]\times 100\%$
- CL_{ss}/F Apparent plasma clearance

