4.2.2 Pharmacokinetic parameters (Parts A & B)

All PK data received will be presented in data listings, and summaries will be presented for patients in the PK analysis set. Data from patients excluded from the PK analysis set will be included in the data listings, but not in the summaries. Extra measurements (such as unscheduled or repeat assessments) will also not be included in summary tables, but will be included in patient listings. Presentations will be by treatment as defined previously.

In addition, the plasma concentration data and the PK data will be explored graphically. The following plots will be presented:

- Individual plots of olaparib concentration versus time. Time on x-axis with linear scale, concentration on y-axis with *log scale*. There will be one plot per patient showing 3 profiles, one for each treatment (ie, one for fed state, one for fasted state, and one for olaparib 300 mg bd).
- Individual plots of olaparib concentration versus time. Time on x-axis with linear scale, concentration on y-axis with *linear scale*. There will be one plot per patient showing 3 profiles, one for each treatment (ie, one for fed state, one for fasted state, and one for olaparib 300 mg bd).
- Geometric mean (\pm geometric SD, if appropriate) of olaparib plasma concentration versus time. The geometric mean for each treatment (ie, fed state, fasted state, and olaparib 300 mg bd) to be shown in different symbols. Time on x-axis with linear scale and concentration on y-axis with *log scale*. Repeat and include Fed (A) and Fasted (A) only.

- Geometric mean (\pm geometric SD, if appropriate) of olaparib plasma concentration versus time. The geometric mean for each treatment (ie, fed state, fasted state, and olaparib 300 mg bd) to be shown in different symbols. Time on x-axis with linear scale and concentration on y-axis with *linear scale*. Repeat and include Fed (A) and Fasted (A) only.
- Individual plots of olaparib concentration versus time. Time on x-axis with linear scale, concentration on y-axis with *log scale*. All patient profiles for fed state on one plot, repeat for fasted state with patient profiles on one plot. Part A data only.
- Scatter plot of AUC, AUC_{0-t} and C_{max} on separate plots presenting ratio of fed : fasted with patient number denoted on x-axis.
- Geometric mean and 90% CI for the ratio of fed : fasted, plotted separately for AUC, AUC_{0-t} and C_{max}

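### The PK analysis set is defined by Part A profiles only but also governs the Part B PK summaries, so a patient whose only evaluable profile is Day 5 is listed and not summarised

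*SAP*

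**What the plan says.** Section 2.1 of the SAP sets up three analysis sets: safety, PK and QT. To enter the PK set a patient must receive olaparib and "provide evaluable PK profiles in at least 1 treatment period i.e. fed (A) or fasted (A"). Part B is not named. The QT set, defined in the same section, does name it: a patient can qualify on data "or time matched between Day -1(baseline) and Day 5 for Part B".

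Part B PK is planned output. Section 3 states that "Multiple-dose PK parameters will be calculated for olaparib on Day 5 of Part B" and that "All PK parameters for Parts A & B will be summarised descriptively". Table 2 gives reporting precision for the steady-state parameters.

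The section that produces these summaries is headed "4.2.2 Pharmacokinetic parameters (Parts A & B"). It says that "summaries will be presented for patients in the PK analysis set" and adds: "Data from patients excluded from the PK analysis set will be included in the data listings, but not in the summaries".

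Section 2.2 allows PK sampling to be omitted for a treatment period after early vomiting. It then says: "The patient may continue in the study and proceed with Part A, if applicable, and then on to Part B and Part C".

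**The concern.** The set is defined on one part of the study and applied to two. A patient can therefore have a complete, evaluable steady-state profile on Day 5 and still fall outside the Part B PK summaries, because of what happened to the Part A samples. No fourth set exists for Part B PK, so nothing else in the plan brings such a patient back in.

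At stake is whether the Part B steady-state tables include every patient who can contribute to them. There is also a procedural cost. If the case arises, the team must either follow the text and leave out a valid profile, or depart from the text after seeing the data.

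**Working it through.** **1. The plan's own figure, as background.** Inputs from Section 1.3: within-patient SD of log AUC 0.26, true food effect 5%, 42 evaluable patients, 90% confidence interval, limits 0.80 to 1.25, power 90%. For a two-period crossover:

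- SE = 0.26 × √(2/42) = 0.0567, with 42 − 2 = 40 degrees of freedom.
- Power is the probability that both one-sided 5% tests against ln 0.80 and ln 1.25 succeed, integrated over the chi-square distribution of the residual variance.
- True ratio 0.95: power 90.8%, and the smallest even n reaching 90% is 42.
- True ratio 1.05: power 91.4%, and the smallest even n reaching 90% is 40.

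The stated 42 patients and 90% power reproduce. Entering 48 allows for 6/48 = 12.5% non-evaluable. None of this depends on how Part B patients enter the PK set.

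**2. The rule, traced through the sections.**

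| Step | Section | Consequence |
|---|---|---|
| Entry to the PK set | 2.1 | Needs an evaluable fed (A) or fasted (A) profile; the i.e. closes the list |
| Day 5 parameters | 3 | Calculated and summarised descriptively |
| Set used for summaries | 4.2.2 (Parts A and B) | PK analysis set |
| Patients outside the set | 4.2.2 | Listings only |
| Reaching Part B without a Part A profile | 2.2 | Possible: sampling may be omitted and the patient may continue |

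Take a patient with fed (A) not evaluable, fasted (A) not evaluable and Day 5 (B) evaluable. Section 2.1 keeps the patient out of the set, and Section 4.2.2 then lists the Day 5 data without summarising them. One evaluable Part A profile is enough to avoid this.

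**3. Size.** The SAP gives no rate of non-evaluable Part A profiles, so the rate p per profile is an assumption. If the two profiles fail independently, the expected number of 48 patients with neither evaluable is 48 × p²:

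- p = 5%: 48 × 0.0025 = 0.12
- p = 10%: 48 × 0.01 = 0.48
- p = 20%: 48 × 0.04 = 1.92

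The figure reaches one patient at p = √(1/48) = 14.4%.

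A reference point comes from the plan's own allowance. If the whole 12.5% were patients with at least one failed Part A profile, then 1 − (1 − p)² = 0.125, so p = 1 − √0.875 = 6.5%, and 48 × 0.0646² = 0.20 patients.

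Under independence these are upper figures for lost Day 5 profiles, because some patients with no Part A profile will not reach Part B or will not give an evaluable Day 5 profile. If failures cluster within patients, the figures would be higher. The SAP offers no basis for putting a number on that.

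**The case against.** **The term treatment period may include Part B.** Section 3 divides the treatment period into Parts A, B and C for adverse events, and Section 4.1 speaks of a treatment period in Part B. On that usage the authors may have meant Day 5 to count. But the PK set definition spells out its own meaning and stops at the two Part A conditions. What stands is that the omission was probably unintended, which is a reason to correct the sentence.

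**Section 2.2 leaves room for judgement.** Patients with partial data are assessed case by case, and a patient with only a Day 5 profile arguably fits. The text does not say that this overrides the definition in Section 2.1, so it makes exclusion less certain without removing the gap.

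**The route is narrow.** This stands. One vomiting episode affects one treatment period and leaves the other Part A profile. Section 2.2 also says only that the patient may continue, so passage to Part B is permitted and not assured.

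**Two stronger readings are not supported.**

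- A reader might infer that Part B protocol deviations are not covered, because the exclusion sentence in Section 2.1 refers to treatment periods. Section 2.2 has a general rule, not limited to Part A, that removes PK data affected by an important deviation from summaries and analyses. A Day 5 deviation is handled there.
- A reader might infer that this gap is what makes the Part B QT and PK summaries rest on different patients. The two sets require different data, a time-matched ECG value and an evaluable PK profile, so they can differ under any wording of the PK set. The pooled ECG work with PK/PD modelling is left to separate methodology (Section 4.1).

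**Conclusion.** The inconsistency between Sections 2.1 and 4.2.2 is real and rests on the text alone. Followed literally, the plan leaves an evaluable Day 5 profile out of the Part B PK summaries when neither Part A profile is evaluable.

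It is a minor point. With independent failures, the expected loss is below one patient unless more than about 14% of Part A profiles fail, which is an assumed scale and not a figure from the SAP. Only descriptive Part B summaries are touched, and no data are discarded, since the listings keep them. The food-effect analysis in Section 4.2.3 uses Part A profiles only, so a patient with none has nothing to add to it. Its conclusion and the sample size do not change.

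**What to change.** In Section 2.1, define the PK analysis set as all patients who receive olaparib and have at least one evaluable profile among fed (A), fasted (A) and Day 5 (B). State that each evaluable profile contributes to its own summary, so that a Day 5 profile enters the Part B tables whatever the status of the Part A profiles, and the Part A tables stay as they are. A separate Part B PK set, used for the Part B summaries in Section 4.2.2, would serve equally well.

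The cost is one sentence. It needs no new data, no change to the food-effect model and no new sample-size calculation. It is best made before the Parts A and B database lock.
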